VI.1 *How many adult subjects do you expect to consent or enroll for this project?*
20

VI.2 **What is the age of the youngest adult subject?**

18.0

VI.3 **What is the age of the oldest adult subject?**

50.0

VI.4 **What is the percentage of adult male subjects?**

0

VI.5 **What is the percentage of adult female subjects?**

100

VI.6 **How many minor subjects do you expect to consent or enroll for this project?**

0

VI.13 **Describe EACH of your subject populations**

- *Include description of any control group(s)*
- *Specify the Inclusion/Exclusion criteria for EACH group*

INCLUSION CRITERIA: In this study we are recruiting women who have had preeclampsia in the past 5 years. Post-partum women, 18 years or older, who have delivered within 5 years of the study visit and who have had a preeclamptic pregnancy diagnosed by their obstetrician and confirmed according to the American College of Obstetricians and Gynecologists criteria for preeclampsia. [This information will be self-reported by the subjects.] Because losartan can have dangerous effects on a fetus, women enrolled in this study will be required to use an effective form of birth control [hormonal patch, implant or pill; intrauterine device; consistent use of barrier contraceptive; or prior medical procedure to prevent pregnancy (i.e. tubal ligation, or vasectomy in current partner)].

EXCLUSION CRITERIA: We exclude participants for skin diseases, current tobacco use, diagnosed or suspected hepatic or metabolic disease including chronic kidney disease (CKD) defined as reduced eGFR < 60 mL/min/1.73m², statin or other cholesterol-lowering medication, current antihypertensive medication, history of hypertension prior to pregnancy, history of gestational diabetes, currently pregnant or planning to become pregnant in the next 6 months, currently breastfeeding, body mass index <18.5 kg/m², allergy to materials used during the experiment (e.g. latex), known allergies to study drugs.

VI.14 **Provide an estimate of the total number of subjects that would be eligible for inclusion in each of your study populations (include your control population if applicable)**

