We will recruit subjects from Johnson and surrounding counties in Iowa. According to the Iowa Department of Public Health, Johnson county has a live birth rate of 11.7/1,000 residents or ~1,750 live births per year. Surrounding counties range from 9.6-12 live births/1,000, adding ~4,000 additional live births annually within the geographical area of reach. Assuming an average rate of 7% for preeclampsia incidence, approximately 400 women would be eligible to participate in the preeclamptic group each year. We will recruit women within 5 years postpartum so we estimate that there are approximately 2,000 eligible participants in our geographic area at any given time.

VI.15 **Describe how you will have access to each of your study populations in sufficient number to meet your recruitment goals.**

We will advertise for participants by posting fliers in the community and in clinicians offices where permission has been granted (see attached flier). We will also post this flier in digital spaces such as on Facebook, Instagram, twitter, and Iowa City Mom's blog (see IC Mom Ad). Participants will be recruited from the University of Iowa and Iowa City, Iowa by mass email (see attached mass email text) and the Noon News (see attached Noon news posting) a newsletter available on campus at UIHC. We will also recruit participants through Research Match. Lastly, we will recruit participants through the Maternal Fetal Tissue Bank (IRB#200910784). We will obtain the contact information and pregnancy history of the registry participants and reach out to eligible volunteers with the approved recruitment materials (email, flyer, phone call). All individuals interested in participating will be directed to contact research staff by phone or email. All individuals interested in the study will be invited to complete the RedCap eligibility survey sent via email. If an individual appears to be eligible for the study based on their RedCap Eligibility survey responses, a member of the research team will contact them via phone or email to tell the individual more about the study, answer any questions, and perform a phone screening to determine eligibility.

VI.16 **Do you plan to recruit/enroll non-English speaking people?**

No

VI.18 **Do you propose to enroll any of the following in this study as subjects?**

- *Employee of the PI or employee of a research team member*
- *Individual supervised by PI or supervised by member of research team*

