VII.D.1.a *Will any of the materials/methods below be used by researchers (or their colleagues) to recruit subjects into this study?*

- the potential subject is a patient OR*
- use of any information considered to be Protected Health Information (PHI) OR*
- review of patient/clinic records be used in recruiting subjects*

Yes

VII.D.1.b *Describe source of records*

Patient EPIC records will be reviewed and screened for suitability. Potential subjects name, contact information, age, and pregnancy history will be reviewed. This will be accomplished by starting with a TriNetX exchange utilizing ICD9 and 10 codes and inclusion criteria to obtain MRN.

VII.D.1.c *Select all Private Identifiable Information (PII) or Protected Health Information (PHI) accessed and used for this study (select all that apply)*

Identify types of PHI accessed

Type of PHI

Data source

Name	
Street address	
City	
County	
Precinct	
Zip code	
Geocodes smaller than state	
Date of birth, ages > 89 years of age	
Diagnosis dates	
Procedure dates	
Admission or discharge dates	
Telephone numbers	

Type of PHI	Data source
Fax numbers	
E-mail addresses	
Social Security number	
Medical record number	
Health plan beneficiary or account numbers	
Certificate/license numbers	
Vehicle identifiers and serial numbers or license numbers	
Device identifiers or serial numbers	
Web URLs	
Internet Protocol (IP) address numbers	
Biometric identifiers including finger/voice prints	
Full face photographic images or any comparable images	
None of the above	

VII.D.2.a *List ALL of the variables, including any identifiers not previously entered or links to identifiers you plan to obtain/use for purposes of this study. (The information accessed should be the minimum data variables necessary for performing the desired analysis.)*

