Name, age, pregnancy history (including preeclampsia diagnoses in the past 5 years), pregnancy status, and current medication use. We will also need to look at data elements that correspond with our exclusion criteria including skin diseases, current tobacco use, diagnosed or suspected hepatic or metabolic disease including chronic kidney disease (CKD) defined as reduced eGFR < 60 mL/min/1.73m², statin or other cholesterol-lowering medication, current antihypertensive medication, history of hypertension prior to pregnancy, history of gestational diabetes, currently pregnant or planning to become pregnant in the next 6 months, currently breastfeeding, body mass index <18.5 kg/m², allergy to materials used during the experiment.(e.g. latex), known allergies to study drugs.

VII.D.3 *Describe why you could not practicably recruit subjects without access to and use of the information described above*

The study requires the subject to meet very specific inclusion/exclusion criteria on their diagnosis. It is easier on the subject to determine this by reviewing their medical records. It will save the subject the time and effort coming to the study site just to learn the do not qualify based on current information.

VII.D.4 *Describe why you could not practicably obtain authorization from potential subjects to review their patient or clinic records for recruitment purposes.*

Without reviewing the medical record information pertaining to inclusion/exclusion criteria we would not be able to identify subjects who may qualify. By reviewing the potential subject's medical record and identifying possible inclusion/exclusion criteria, the study team will be able to determine if a subject has a possibility of qualifying which may save the subject and study team the time and effort to participate in a visit that may result in the subject not qualifying. Also, it would not be practicable to approach all individuals presented at the clinic to ask if their medical record could be reviewed to determine eligibility for the research.

VII.D.5 *Describe plans to protect the identifiers from improper use or disclosure*

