Contact information is required to contact the subjects after the phone screening in case the research staff needs to reschedule Visit 1 or for follow up if the subject does not show for the Visit 1. Because this study is recruiting using mass email, subject information including a brief description why they were deemed ineligible (i.e. health history, medication, breastfeeding) will be kept to prevent making contact twice with an individual who is ineligible. Information on why a potential subject is ineligible/not passing the phone screening is to report to NIH and to monitor our recruiting progress. Information on how the subjects heard of the study will help the research team understand the most successful methods for advertising for the study.

VII.D.23 Will this information be shared with anyone outside the UI research team members?

No

VII.D.25 *After the subject agrees to participate (signs consent), are there any screening procedures, tests, or studies that need to be done to determine if the subject is eligible to continue participating?*

Yes

VII.D.26 *List and describe screening*

Complete the additional info survey (see attached RedCap document "additional info survey") for study records
 Medical history and physical exam
 Resting blood pressure and heart rate
 Standard blood chemistries (lipids, complete blood count, basic metabolic panel, liver enzymes)
 Urine pregnancy test

VII.D.27 *Discuss how much time a potential subject will have to agree to consider participation and whether or not they will be able to discuss the study with family/friends before deciding on participation.*

There is no time limit for the subject to agree to consider to be in the study as long as the study is actively recruiting subjects and they are still eligible. Subjects are allowed to discuss the study with family/friends before deciding on participation.

VII.D.28 *How long after the subject agrees to participate do study procedures begin?*

The procedures in visit 1 (screening visit) can occur on the same day as consent. The experimental visits (pickup and begin oral treatment) will begin within 1-2 weeks or less of visit 1.

VII.D.29 *Provide a description of the enrollment and consent process for adult subjects*

- *Describe each study population separately including control population*
- *Include when recruitment and consent materials are used*

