VII.E.2 *Describe randomization scheme/assignment including ratio such as 1:1, 2:1 etc.*
Subjects will be randomized to which treatment they receive first (placebo or losartan). All subjects will complete both arms of the study. They will be blinded to which treatment they are receiving at the time of the treatments. If they wish to know, subjects can be informed which treatment they received at what time when they complete the study.

VII.E.3 *Will any questionnaires, surveys, or written assessments be used to obtain data directly from subjects in this study?*
Yes

VII.E.4 *List all questionnaires, surveys, written assessments and ATTACH each one to the application. (NOTE: You are NOT prohibited from attaching copyrighted materials to this application)*
pre-consent screening survey
additional information survey
health history questionnaire

VII.E.5 *Does this project involve creating any audiotapes, videotapes, or photographs?*
No

VII.E.6 *Provide a detailed description in sequential order of the study procedures following the consent process - DO NOT cut and paste from the Consent Document.*

Describe study populations separately if they will be participating in different procedures - include CONTROL population if applicable.

DESCRIBE:

- *What subjects will be asked to do/what happens in the study (in sequential order)*
- *The time period over which procedures will occur*
- *The time commitment for the subject for individual visits/procedures*
- *Long-term followup and how it occurs*

Visit 1 - Consent and Screening (approximately 1 hour)

The PI or research staff explain the study and go over the informed consent with the participant. After the participant signs the informed consent, the PI or research staff performs the physical screening that includes urine pregnancy test, heart rate (HR), blood pressure (BP), height, waist circumference, and weight measurements. The participant fills out the health history questionnaire and confirms that they are using an effective form of birth control. A research nurse performs or approved laboratory personnel standard venipuncture to obtain blood (total = 7.5ml blood) for complete blood count (CBC), chemistry analysis, and lipid profile to be measured at UIHC pathology labs. The subject provides a urine sample for the measurement of urine proteins which will be measured by the UI Diagnostic Lab.

Visits 2 and 5- Pick up study medications (approximately 15 minutes)

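### Preeclampsia is described as confirmed by ACOG criteria but taken from self-report; women recruited by advertisement can enter with no record check, and no route is stated to apply the criteria

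*Combined protocol and SAP*

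**What the plan says.** Section VI.13 admits women with a preeclamptic pregnancy that an obstetrician diagnosed. It describes the diagnosis as "confirmed according to the American College of Obstetricians and Gynecologists criteria for preeclampsia. [This information will be self-reported by the subjects".

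Other sections describe different sources for the same fact:

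- **Medical records.** Section VII.D.1.b: "Patient EPIC records will be reviewed and screened for suitability". This starts from a TriNetX search on ICD codes. Section VII.D.2.a lists among the variables to be obtained "pregnancy history (including preeclampsia diagnoses in the past 5 years", and section VII.D.3 says of the diagnosis-related criteria: "It is easier on the subject to determine this by reviewing their medical records".
- **Tissue bank registry.** Section VI.15: "We will obtain the contact information and pregnancy history of the registry participants".
- **Advertisement, email and ResearchMatch.** Section VI.15: "All individuals interested in the study will be invited to complete the RedCap eligibility survey sent via email". A phone call follows (VI.15, VII.D.20, VII.D.29).

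Post-consent screening (VII.D.26) lists a survey, "Medical history and physical exam", resting blood pressure and heart rate, blood tests and a urine pregnancy test. Visit 1 (VII.E.6) adds body measurements, a health history questionnaire and urine protein.

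On design, section VII.E.2 states: "All subjects will complete both arms of the study". Section XI.2 calculates that 10 subjects are needed and plans 20, expecting about 5 screen failures and about 5 dropouts.

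**The concern.** A woman can report that she was told she had preeclampsia. Her report cannot show that the blood pressure and laboratory findings of that pregnancy met a professional society's criteria. If the bracketed sentence is the operating rule, the condition that defines the study population is unverified for anyone without a record behind her, and the strength of evidence depends on how she was recruited.

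All three hypotheses in section I.5 are about women who had preeclampsia, and the second and third rest on an exaggerated response to angiotensin II in them. A woman who had gestational hypertension only, or who misremembers her diagnosis, may lack that mechanism. With about 10 completers, each such woman is 10% of the data. At stake are the population the result describes and, possibly, the size of the effect.

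**Working it through.** **Step 1: is there a record check for each route?**

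| Route | Source of the diagnosis | Stated check against ACOG criteria |
|---|---|---|
| EPIC/TriNetX (VII.D.1.b, VII.D.2.a, VII.D.11) | ICD codes and chart review | None |
| Tissue bank (VI.15, VII.D.1) | Registry pregnancy history | None |
| Fliers, social media, mass email, ResearchMatch (VI.15, VII.D.20, VII.D.29) | REDCap survey and phone call | None |

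The listed post-consent procedures do not fill the gap. They record present status or the woman's own account. Section I.6 says the clinical signs typically resolve within 12 weeks of delivery, and women may be up to 5 years postpartum, so current blood pressure or urine protein cannot establish the past diagnosis.

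**Step 2: the plan's own sample size (XI.2).** The recruitment arithmetic reproduces: 20 − 5 − 5 = 10 completers. The power statement does not. It gives an effect of 15% between microdialysis sites, power 0.08 and α = 0.05, with no SD or within-woman correlation. I assume 0.80 was meant, a two-sided test, and a paired t-test as the nearest simple form. With standardized paired effect d (mean difference divided by SD of differences) and n women,

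power = P(|T| > t(0.975, n − 1)), where T is noncentral t with n − 1 degrees of freedom and noncentrality d√n.

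Solving for 80% at n = 10 (critical value 2.262) gives d = 0.996, noncentrality 0.996 × √10 = 3.15. Power of 0.08 taken literally would correspond to d = 0.18. So 80% at n = 10 is a working assumption. The plan states it neither in those terms nor for losartan versus placebo.

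**Step 3: illustrative dilution.** Let k of the 10 women be misclassified and have a fraction r of the true response. The mean effect is multiplied by 1 − k(1 − r)/10. Power is simulated with d = 0.996 in the 10 − k true cases, 0.996r in the other k, and unit SD, so the added spread between women is included.

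| Misclassified, k | r = 0: effect, power | r = 0.5: effect, power | r = 0.75: effect, power |
|---|---|---|---|
| 0 | 100%, 80% | 100%, 80% | 100%, 80% |
| 1 | 90%, 68% | 95%, 75% | 97.5%, 78% |
| 2 | 80%, 55% | 90%, 70% | 95%, 76% |
| 3 | 70%, 42% | 85%, 64% | 92.5%, 73% |

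Neither k nor r is in the documents.

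**Step 4: power after dropping unconfirmed women.** The Step 2 formula with d = 0.996 gives 68% at n = 8 and 60% at n = 7.

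**Step 5: timing.** This version was approved 7/19/2024 and VII.B.1.c dates the last visit 08/31/2024, 43 days later. Two 6-week periods and a washout of at least 14 days (VII.E.6) take 6 + 6 + 2 = 14 weeks, or 98 days. On these dates a newly enrolled woman could not finish, so a check would mostly be retrospective.

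**The case against.** The sentence in VI.13 has a milder reading: the obstetrician both diagnosed and confirmed the condition at the time, and the bracket only says how the team learns of it. On that reading nobody confirms her own laboratory values. This is fair, and it turns a flat contradiction into an ambiguity. It does not supply a check, and the sentence still disagrees with the sections that take the diagnosis from records.

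The survey and questionnaires are attachments that are not reproduced, so they may ask about blood pressure or proteinuria in the pregnancy. The answers would still be self-report.

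A reader might infer three stronger conclusions, which the documents do not support:

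- *The whole cohort rests on self-report.* The EPIC/TriNetX and tissue bank routes bring a recorded diagnosis or pregnancy history.
- *The losartan-placebo comparison is biased.* Each woman receives both treatments, so misclassification does not bias the contrast among those enrolled.
- *Power falls to 68%, 55% or 42%.* Those figures need a zero response in every misclassified woman and 80% power for losartan versus placebo. The documents do not support the first, and the plan does not state the second: XI.2 concerns a difference between microdialysis sites. With half or three-quarters of the response the loss is much smaller.

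It is also true that removing unconfirmed women can cost more than it gains: 68% at n = 8 is slightly below the 70% from keeping two half-responders, and 60% at n = 7 is below the 64% from keeping three.

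**Conclusion.** The point holds as a verification gap in the study's defining criterion. Section VI.13 claims confirmation by ACOG criteria and sources it to self-report; women from advertisements, email and ResearchMatch can enter without a record check; and no route is stated to apply the criteria. This goes beyond missing detail, because the stated rule allows the condition to go unverified while the team already has record access for other women.

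The consequence is an uncertain target population and a possible dilution of unknown size. Across one to three misclassified women and responses from zero to three-quarters, illustrative power runs from 78% down to 42%. That range rests on 80% power at n = 10, a two-sided paired t-test and assumed values of k and r. It shows sensitivity and is not an estimate of what happened in this trial. The inconsistency between sections stands without any of these figures.

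**What to change.** Replace the bracketed sentence in VI.13 with a rule that covers every recruitment route: the preeclampsia diagnosis is checked, with the woman's consent, against the delivery record for the ACOG criteria, using EPIC or the registry where the record is held and a signed record release otherwise. For any new enrollee this is done before study drug is given; for women already treated it is done retrospectively, before analysis. Reconcile VI.13 with VI.15, VII.D.1.b, VII.D.2.a and VII.D.3 so that they name the same source.

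In XI.1, add that all women stay in the primary analysis, that the number record-confirmed is reported, that women without a record are flagged as self-report only, and that a sensitivity analysis is limited to record-confirmed women.

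Cost: a short chart check or record release for about 15 enrolled women (20 − 5), and some delay for those who delivered elsewhere. Nobody need be excluded for lack of a record. The sensitivity analysis has lower power (Step 4), so it should be read for consistency of the estimate and not as a second test.

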The PI or research staff give the participant study medication (losartan or placebo). The PI or research staff goes over the instructions for taking the study medication which includes how many pills to take and at what times of day, potential side effects, and who to call if they have questions or problems while taking the medication.

Visits 3 and 6 - Pick up 24 hour blood pressure monitor (approximately 15 minutes)

The PI or research staff instrument the participant with the 24 hour blood pressure monitor. The PI or research staff goes over the instructions for wearing the monitor.

Visits 4 and 7 - Experimental visits (approximately 4 hours each)

Note: prior to coming to PSRB for the experimental visits, subjects take the oral study medication for 6 weeks. Subjects will ingest 1 pill per day. After the first study visit, subjects will undergo a washout period of at least 14 days in which they do not ingest any study medication, before beginning the same 6 week regimen of the other treatment.

In the event of an experimental failure (e.g. equipment stops working, building power outage during study visit, etc) subjects may be asked to repeat a trial.

Experimental procedures

24 hours before the study visit, subject will be instrumented with a 24 hour blood pressure monitor to wear home for 24 hours. Subject will return the blood pressure monitor to the investigators when they come in for the experimental visit.

Subjects will come to the CRU or 118 PSRB where a research nurse or approved laboratory personnel performs a blood draw (14.5 ml, < 1 Tablespoon) for substances of interest (e.g. inflammatory cytokines) and immune cell activity, and blood chemistry. The subject provides a urine sample for the measurement of urine proteins which will be measured by the UI Diagnostic Lab. Then the rest of the study visit occurs in 118 PSRB for the experiment (Pulse wave velocity and intradermal microdialysis).

Pulse wave velocities (PWV) on Carotid-femoral and carotid-brachial: Carotid-femoral artery PWV, the 'gold standard' in vivo assessment of aortic

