stiffness in humans, will be assessed by applanation tonometry using the Sphygmocor pulse wave analysis system (AtCor Medical, Inc.) as previously described by the PI.45-47 After 10 minutes of supine rest, carotid, brachial, and femoral artery pulse waveforms will be recorded non-invasively by sequentially recording of carotid, brachial, and femoral artery pulse waveforms with a hand-held transducer for 20 seconds. Pressure waveforms are gated to the 13 lead ECG R wave in order to calculate the transit time (t) between the foot of the carotid and the femoral waveforms.^{85, 86} The carotid-femoral and carotid-brachial transit distance (CFTD) is estimated between the 2 anatomical sites as the difference between the suprasternal notch (SSN) to carotid (SSN-C) and femoral (SSN-F) sites. Thus, the CFTD=(SSN-F)-(SSN-C) and PWV calculated as CFTD/t. This approach accounts for parallel transmission of the pulse wave up the brachiocephalic and carotid arteries, and simultaneously along the aortic arch using the SSN as a fiducial point where parallel transmission begins (e.g., bifurcation site of aortic arch/brachiocephalic artery).

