The -80C freezer in 111 PSRB is a shared wet lab space. The door to this lab space is kept locked but those with keys to the shared lab space would be able to enter the room. Individuals with key access to 111 PSRB include:

[name]
[name], BS
[name], BA

X.7***Does your study meet the NIH criteria for a [Certificate of Confidentiality](#) or will you be applying for Certificate of Confidentiality?***

Yes

X.8***If yes, provide rationale:***

Per Section 2012 of the 21st Century Cures Act as implemented in the 2017 NIH Certificates of Confidentiality Policy, all ongoing or new research funded by NIH as of December 13, 2016 that is collecting or using identifiable, sensitive information is automatically issued a CoC.

XI. Data Analysis**XI.1*****Describe the analysis methods you will use, including, if applicable, the variables you will analyze***

The primary outcome variable will be cutaneous vascular conductance, which is calculated from laser-Doppler flux/mean arterial pressure. Three-way repeated measures ANOVA (treatment, MD site, dose) will be used to examine systemic treatment differences (losartan vs. placebo) and local

microdialysis treatment differences across the doses of pharmacological stimuli. Appropriate post-hoc analyses with corrections for multiple comparisons will be performed when main effects are identified, including potential confounding variables as covariates. Paired t-tests will be used to examine systemic treatment differences on pulse wave velocity.

XI.2***Provide the rationale or power analysis to support the number of subjects proposed to complete this study.***

Based on previous data examining chronic pharmacological intervention strategies we calculate that 10 subjects will be necessary to detect an effect size of 15% between microdialysis sites (1 sample RMANOVA, power=0.08, $\alpha=0.05$). Based on the duration of the intervention and prior experience, we anticipate that ~5 subjects will screen but not be eligible and of those that enroll, ~5 will drop out of the intervention, therefore, we suggest a total sample of 20 subjects.

XII. Future Research**XII.1*****Do you wish to keep any information about subjects involved with this research project so that members of the current research team may contact them in the future for your own research projects?***

Yes

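### Carotid-brachial pulse wave velocity is given the femoral distance and femoral transit time, so as written it equals carotid-femoral pulse wave velocity

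*Combined protocol and SAP*

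**What the plan says.** The procedures in VII.E.6 announce two segments: "Pulse wave velocities (PWV) on Carotid-femoral and carotid-brachial". Three waveforms are taken: "carotid, brachial, and femoral artery pulse waveforms will be recorded non-invasively".

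From there the section gives one of everything.

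- **Transit time:** the waveforms are used to "calculate the transit time (t) between the foot of the carotid and the femoral waveforms". No carotid-to-brachial time is defined.
- **Distance:** one quantity is named for both segments, "The carotid-femoral and carotid-brachial transit distance (CFTD) is estimated between the 2 anatomical sites". It is constructed as "the difference between the suprasternal notch (SSN) to carotid (SSN-C) and femoral (SSN-F) sites". No distance from the suprasternal notch to the brachial site appears.
- **Formula:** "Thus, the CFTD=(SSN-F)-(SSN-C) and PWV calculated as CFTD/t".

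Section XI.1 then says "Paired t-tests will be used to examine systemic treatment differences on pulse wave velocity", without naming a segment. The primary outcome in XI.1 is cutaneous vascular conductance. VII.B.11 states that no separate written protocol accompanies the form.

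**The concern.** A pulse wave velocity is a path length divided by the time the wave takes to travel that path, and both terms must belong to the same arterial segment. Here the distance sentence expressly covers the carotid-brachial segment and gives it femoral landmarks, and the only t defined ends at the femoral artery. So this is more than a missing detail: the stated rule, applied to carotid-brachial PWV, gives the wrong quantity.

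At stake is whether a reported carotid-brachial PWV means anything. It could duplicate the carotid-femoral value, or it could mix a femoral distance with a brachial time. A reader of the results could not tell which. PWV is also the only outcome besides cutaneous vascular conductance for which XI.1 names a test.

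**Working it through.** The documents give no PWV value, distance, transit time or standard deviation, so there is no stated figure to reproduce. The check is definitional, followed by an illustration on assumed values.

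**Notation.** F, C and B are the distances from the suprasternal notch to the femoral, carotid and brachial sites (SSN-F, SSN-C, SSN-B). t_cf and t_cb are the carotid-to-femoral and carotid-to-brachial transit times. VII.E.6 defines F, C and t_cf. It defines neither B nor t_cb.

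**Step 1: what each segment needs, using the plan's own subtraction method.**

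- Carotid-femoral: (F − C)/t_cf. This is what VII.E.6 states, and it is consistent.
- Carotid-brachial: (B − C)/t_cb. Neither B nor t_cb is in the documents.

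**Step 2: literal reading.** Carotid-brachial PWV = (F − C)/t_cf, which is carotid-femoral PWV. The two measures coincide in every woman and both periods, so a paired t-test on each would be the same test twice. This step needs no assumptions.

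**Step 3: mixed reading.** Suppose staff use t_cb but keep the stated distance. The result is (F − C)/t_cb, which is the segment-specific value multiplied by k = (F − C)/(B − C). With distances unchanged between periods, a woman's losartan-placebo difference is multiplied by the same k. k exceeds 1 whenever F exceeds B.

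**Step 4: size of k under assumed distances (cm), pairing longer femoral with longer brachial distances.**

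| C | F | B | k |
|---|---|---|---|
| 8 | 50 | 35 | 42/27 = 1.56 |
| 8 | 55 | 40 | 47/32 = 1.47 |
| 8 | 60 | 45 | 52/37 = 1.41 |
| 10 | 55 | 35 | 45/25 = 1.80 |
| 10 | 60 | 40 | 50/30 = 1.67 |
| 10 | 65 | 45 | 55/35 = 1.57 |

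The range is about 1.4 to 1.8.

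**Step 5: the three versions in m/s, with C = 0.10 m and assumed times.**

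| F, B (m) | t_cf, t_cb (s) | Literal (F − C)/t_cf | Mixed (F − C)/t_cb | Segment-specific (B − C)/t_cb |
|---|---|---|---|---|
| 0.55, 0.35 | 0.070, 0.035 | 6.43 | 12.86 | 7.14 |
| 0.60, 0.40 | 0.070, 0.035 | 7.14 | 14.29 | 8.57 |
| 0.65, 0.45 | 0.080, 0.040 | 6.88 | 13.75 | 8.75 |
| 0.60, 0.40 | 0.060, 0.030 | 8.33 | 16.67 | 10.00 |

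In these examples the literal formula falls below the segment-specific value and the mixed formula lies well above it. The direction of the error therefore depends on which reading staff follow.

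**The case against.** The strongest reply is that this is a drafting slip. The word carotid-brachial looks inserted into existing carotid-femoral text, since the abbreviation CFTD was left unchanged. A brachial waveform is recorded, which would serve no stated purpose if only the femoral transit time were wanted. The section also refers to earlier descriptions of the method, and trained staff may well measure the right distance. This stands as far as conduct goes. A reader might infer that no notch-to-brachial distance was ever taken and that wrong values are in the data; the documents show only that none is written down. But a reference to earlier work, which is not available here, does not override a formula written out in the plan, and VII.B.11 says there is no separate protocol to correct it.

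Three further inferences go too far.

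- **A single inflation factor with a wide range.** Step 4's distances with C = 8 can be paired at opposite extremes to give 42/37 = 1.14 and 52/27 = 1.93. Those pairings are unlikely, because both distances would be expected to rise with body size. In any case the factor applies only to the mixed reading.
- **A seriously distorted paired test.** On the mixed reading k depends on a woman's anatomy and is essentially constant across her two periods, so the sign of her difference is kept. A k common to all women leaves the t statistic unchanged. Only the spread of k between women alters the test, and that effect is minor.
- **Two PWV outcomes, each certain to be tested.** XI.1 names no segment. Two tests are plausible given VII.E.6, but not stated.

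It is also fair to say that PWV is not the primary outcome, is absent from the three hypotheses in I.5, and plays no part in the sample-size statement in XI.2.

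**Conclusion.** The carotid-brachial definition in VII.E.6 is wrong as written. Taken literally it makes carotid-brachial PWV identical to carotid-femoral PWV, a conclusion that rests on the text alone. If a brachial time is combined with the stated femoral distance, the value and its treatment difference in m/s are inflated by (SSN-F − SSN-C)/(SSN-B − SSN-C), roughly 1.4 to 1.8. That range rests entirely on the assumed distances shown.

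The point is confined to this one measure, which is not primary. Carotid-femoral PWV is soundly defined and cutaneous vascular conductance is untouched. The documents support a finding about the definition. They do not support a finding that the recorded data are wrong. The correction is still worth making, because it is cheap and because without it a reported carotid-brachial value cannot be interpreted.

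**What to change.** 1. In VII.E.6 keep carotid-femoral PWV = [(SSN-F) − (SSN-C)]/t(carotid to femoral), and add a separate definition: carotid-brachial PWV = [(SSN-B) − (SSN-C)]/t(carotid to brachial).
2. Record SSN-B at least once per woman and use the same distance in both periods. A repeat at every visit is not needed for the crossover comparison.
3. In XI.1 state which PWV segment or segments the paired t-test covers.
4. VII.B.1.c gives 08/31/2024 as the date of the last visit, so collection may be over. In that case, state which distance and time were used. If SSN-B was recorded, recompute. If it was not, do not report carotid-brachial PWV in m/s from the femoral distance; compare carotid-brachial transit time between treatments, using the recorded carotid and brachial waveforms.

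The cost is one tape measurement per woman and a sentence or two of text.
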